### 14. Pregnancy or lactation

15. Any other disease or condition which, in the judgment of the Investigator, would place a subject at undue risk by being enrolled in the trial, or cause inability to comply with the trial.

# Study Assessments & Schedule

A total of 15 consenting subjects meeting the study eligibility criteria will be enrolled and treated with EPN-701 10 mg (one 10 mg capsule to be taken orally once a day, at the same time each morning), for 14 days.

The expected duration of study participation for an individual subject is approximately five weeks, including up to one week for screening, two weeks of study treatment, and two weeks of post-treatment safety follow-up. Subjects will undergo a total of 14 visits during their study participation: Screening visit (within seven days prior to the first dose of study drug), three visits per week during the two-week treatment, and two-week safety follow-up periods (coinciding with the subject's hemodialysis schedule), and the End-of-Study (EOS)/Early Termination visit. Baseline assessments will be completed prior to the first study drug intake on Day 1. End-of-Treatment (EOT) assessments will be completed after the last dose of study drug on study Day 15 (or earlier in case of an early discontinuation of the study treatment). The EOS/Early Termination visit will occur two weeks after the last dose of study drug (on study Day 29).

Subjects will be monitored for adverse events (AEs), and concomitant medications will be recorded throughout their study participation (from screening through the EOS/Early Termination Visit). Additional safety assessments will include: physical examinations, safety laboratory tests (hematology, including complete blood count [CBC]; complete metabolic panel [CMP, including electrolytes, renal and liver function tests, and lipid profile]; and coagulation panel), vital signs measurements, and 12-lead ECG. In addition, occurrence of dialyzer clotting will be assessed at each dialysis session, and Kt/V (a measure of dialysis adequacy) will be calculated at baseline (as the average of the last three pre-study Kt/V values obtained as part of the subject's standard of care) and at the end of treatment.

Blood for PK assessments will be sampled as follows:

 On Day 1 (baseline) and Day 8 (Week 2, on-treatment): predialysis (at the time of needle placement, denoted as 0 hours), immediately followed by study drug administration, and then at 1 hour (+/- 5 minutes), 2 hours (+/- 5 minutes), 3 hours (+/- 5

minutes), 4 hours (+/- 30 minutes)/before needle removal, 6 hours (+/- 30 minutes), 8 hours (+/- 30 minutes), and 24 hours (+/- 30 minutes), and 24 hours (+/- 30 minutes), and 15: pre-dialysis (at the time of needle placement, at 0 hours), immediately followed by study drug administration, and then at 4 hours (+/- 30 minutes)/before needle removal; and  • On Days 17 (Week 3, off-treatment) pre-dialysis only (at the time of needle placement).  Pre- and post-dialysis blood samples for biomarker analyses will be collected at Baseline, and on select Mondays during the two-week treatment, and two-week safety follow-up periods.  Refer to Table 1, Schedule of Study Activities for further details.  EPN-701 (a new formulation containing highly purified Menaquinone-7 or MK-7 as the active ingredient) is the test product) identity, dose, and mode of administration  EFN-701 (a new formulation containing highly purified Menaquinone-7 or MK-7 as the active ingredient) is the test product in this study, and will be provided by the study sponsor at the following dosage strength:  • 10 mg soft-gel capsule for oral administration.  Each subject will take one 10 mg capsule of EPN-701 per day orally over 14 days.  The study drug is to be taken at the same time each morning.  Not applicable; this is an uncontrolled study.  Wot applicable; this is an uncontrolled study.  Frequency of treatment-emergent AEs and treatment-emergent AEs assessed as related to the study drug (defined as possibly, probably, and definitely related events). A treatment-emergent AE is defined as any AE with an onset between the first dose of the study drug and the last study visit, or any AE with an onset prior to first dose that increases in severity or frequency after the first dose of study drug. Adverse events include both clinical events and laboratory abnormalities that are assessed as clinically significant.  Secondary Safety Endpoints:		
identity, dose, and mode of administration  Efficacy Endpoints  Not applicable  Primary Safety Endpoint:  • Frequency of treatment-emergent AEs and treatment-emergent AEs assessed as related to the study drug (defined as possibly, probably, and definitely related events). A treatment-emergent AE is defined as any AE with an onset between the first dose of the study drug and the last study visit, or any AE with an onset prior to first dose that increases in severity or frequency after the first dose of study drug. Adverse events include both clinical events and laboratory abnormalities that are assessed as clinically significant.	Product (IMP; Test Product) identity, dose, and mode of	
 
hours (+/- 30 minutes), 8 hours (+/- 30 minutes), and 24 hours (+/- 60 minutes) after study drug administration;
 
On Days 3, 5, 10, 12, and 15: pre-dialysis (at the time of needle placement, at 0 hours), immediately followed by study drug administration, and then at 4 hours (+/- 30 minutes)/before needle removal; and
 
On Day 17 (Week 3, off-treatment) pre-dialysis only (at the time of needle placement).
 
Pre- and post-dialysis blood samples for biomarker analyses will be collected at Baseline, and on select Mondays during the two-week treatment, and two-week safety follow-up periods.
 
Refer to Table 1, Schedule of Study Activities for further details.
 
EPN-701 (a new formulation containing highly purified Menaquinone-7 or MK-7 as the active ingredient) is the test product in this study, and will be provided by the study sponsor at the following dosage strength:
 
10 mg soft-gel capsule for oral administration.
 
Each subject will take one 10 mg capsule of EPN-701 per day orally over 14 days.
 

Safety Endpoints  Primary Safety Endpoint:  Frequency of treatment-emergent AEs and treatment-emergent AEs assessed as related to the study drug (defined as possibly, probably, and definitely related events). A treatment-emergent AE is defined as any AE with an onset between the first dose of the study drug and the last study visit, or any AE with an onset prior to first dose that increases in severity or frequency after the first dose of study drug. Adverse events include both clinical events and laboratory abnormalities that are assessed as clinically significant.	identity, dose, and mode	Not applicable; this is an uncontrolled study.
• Frequency of treatment-emergent AEs and treatment- emergent AEs assessed as related to the study drug (defined as possibly, probably, and definitely related events). A treatment-emergent AE is defined as any AE with an onset between the first dose of the study drug and the last study visit, or any AE with an onset prior to first dose that increases in severity or frequency after the first dose of study drug. Adverse events include both clinical events and laboratory abnormalities that are assessed as clinically significant.	Efficacy Endpoints	Not applicable
Frequency of serious adverse events (SAEs), AEs leading to	Safety Endpoints	Frequency of treatment-emergent AEs and treatment- emergent AEs assessed as related to the study drug (defined as possibly, probably, and definitely related events). A treatment-emergent AE is defined as any AE with an onset between the first dose of the study drug and the last study visit, or any AE with an onset prior to first dose that increases in severity or frequency after the first dose of study drug. Adverse events include both clinical events and laboratory abnormalities that are assessed as clinically significant.  Secondary Safety Endpoints:   Secondary Safety Endpoints:

	Changes from baseline in safety laboratory parameters										
	Changes from baseline in vital signs measurements										
	Changes from baseline in ECG parameters.										
Biomarker Endpoints	
 
Secondary Endpoints:
 
Plasma levels of the following biomarkers on Day 15 (end-of-treatment) and Day 22 compared to baseline: uncarboxylated MGP; uncarboxylated osteocalcin; Activated Protein C, and PIVKA-II protein.
 
										
	Exploratory Endpoints:										
	
 
Plasma levels of the following biomarkers on Day 15 (end-of- treatment) and Day 22 compared to baseline: osteoprotegerin, Fetuin A, hs-CRP.
 
										
	Time to Formation of Secondary Calciprotein Particles (T-50 Test), including CPP size.										
Pharmacokinetic	Exploratory Endpoints:										
Endpoints	EPN-701 plasma concentrations (ng/mL) at each measured time-point will be determined according to standard procedures, using a validated high-performance liquid chromatography (HPLC) tandem mass spectrometric (LC/MS/MS) method.										
	In addition, depending on the observed plasma levels, the following PK parameters may be determined for EPN-701:										
	Maximum plasma concentration (C max ) [ng/mL]										
	Time to maximum plasma concentration (T max ) [hr]										
	
 
Area under the concentration-time curve (AUC) from time 0 to 24 hours (AUC0-24 [hr×ng/mL])
 
										
Interim Safety Assessments by the Safety Review Committee (SRC)	A SRC will review the safety data accumulated during the study at regular intervals. The SRC will be comprised of the Sponsor's Medical Monitor, Independent Medical Monitor, and the Principal Investigator. Further details will be provided in the SRC Charter.										
Statistical Methods	Sample Size Calculation  No formal sample size calculation was performed. The selected sample size of 15 subjects is consistent with preliminary safety and PK studies of a similar design and is expected to provide sufficient information to identify safety issues, while limiting subject exposure.										

### **Analysis Populations**

- The safety population will include all subjects who received at least one dose of study drug.
- The PK population will include all subjects who received at least one dose of study drug and have sufficient plasma concentrations data for PK analysis.

### **General Considerations**

- All analyses will be descriptive. Binary and categorical data will be summarized by number and percentage of subjects. Continuous data will be summarized by means, standard deviations (SDs), medians, and ranges (minimum, maximum), as appropriate.
- All data will be included in appropriate per-subject listings.

### Efficacy Analyses

Not applicable.

### Safety Analyses

- Adverse Events: All AEs will be coded using the current version of the Medical Dictionary for Regulatory Activities (MedDRA) and will be included in per-subject listings. In addition, treatment-emergent AEs will be summarized in frequency tables, by MedDRA System Organ Class (SOC) and by Preferred Term (PT). Adverse events assessed as related to the study drug will be summarized in a similar manner. A summary of AEs by maximum severity grade will also be provided.
- Concomitant Medications: All concomitant medications will be coded using the most current version of the World Health Organization (WHO) Drug Dictionary and will be included in per-subject listings.
- Laboratory parameters will be summarized at each time point measured using descriptive statistics, including means, SDs, medians, and ranges, as appropriate. Change from baseline will be summarized similarly, with 95% confidence intervals (CIs) for each change. Shift tables may also be provided, if warranted by the data. All safety laboratory data will be included in appropriate per-subject listings, along with reference ranges, and indication of clinically significant departures from the respective reference ranges.

	ECG parameters: will be included in appropriate per-subject listings and summaries.      Pharmacokinetic Analyses     EPN-701 plasma concentration data will be measured at specific timepoints (see Table 1), tabulated and summarized. Descriptive statistics for plasma concentrations and PK parameters will include arithmetic means and SDs, geometric means and coefficients of variation, medians, and ranges, as appropriate.								
	Biomarker Analyses Biomarkers will be summarized in a similar manner as described for safety laboratory parameters, with summary at each time point along with change from baseline. Depending of the distribution of the biomarkers, transformations to minimize skew and outliers may be performed.								
	Interim Analyses Not applicable.								
Study Duration	Overall Study Duration: All subjects are expected to be enrolled within approximately three months. The end of the study is defined as the last subject last visit (LSLV), which is expected approximately six to seven months after the enrollment of the first subject. The actual length of the study and the time for final analysis will depend on the recruitment rate.								
	Duration of Study Participation Per Subject: The expected duration of the study for an individual subject is approximately five weeks, including up to one week for screening, two weeks of study treatment, and two weeks of post-treatment safety follow-up. Subjects will undergo a total of 14 visits during the study participation.								
Participating Centers	The study will be conducted at one to three dialysis centers in the United States.								

The schedule of study activities is provided in **Table 1** below.

Table 1 Schedule of Study Activities

	WEEK -1	WEEK 1 ON-TREATMENT			WEEK 2 ON-TREATMENT			WEEK 3 POST-TREATMENT			WEEK 4 POST-TREATMENT			EOS/ EARLY
VISIT SCHEDULE	Screening	1 BL	2	3	4	5	6	7 EOT	8	9	10	11	12	TERMINA TION
Study Day	-7 to -1	1	3	5	8	10	12	15	17	19	22	24	26	29
Day of the week		Mon	Wed	Fri	Mon	Wed	Fri	Mon	Wed	Fri	Mon	Wed	Fri	Mon
Informed Consent & HIPAA Authorization	Х													
Demographics [1]	Х													
Medical History [2]	Х													
Disease History [3]	Х													
Physical examination [4]	Х							(X)						Х
Weight and height measurements [5]	Х	Х	Х	Х	Х	Х	Х	Х						Х
Standard 12-lead ECG [6]	Х							Х						Х
Vital signs measurements [7]	Х	Х	Х	Х	Х	Х	Х	Х						Х
Hematology, CMP, Coagulation panel [8]	Х	Х			Х			Х			Х			Х
Testing for HIV, Hepatitis B and C [9]	Х													
Serum β-hCG Pregnancy Test [10]	Х													
Eligibility Criteria	Х	Х												
Concomitant Medications [11]	Х	Х	Х	Х	Х	Χ	Х	Х	Χ	Χ	Х	Χ	Χ	Х
Adverse Event recording [12]		Х	Х	Х	Х	Х	Х	Х	Х	Х	Х	Х	Х	Х
Study drug administration [13]		On	ce daily,	from Da	ay 1 thro	ugh Day	14							
EPN-701 PK assessments [14]		Х	Х	Х	Х	Х	Х	Х	Χ					
Kt/V assessment [15]		Х						Х						
Biomarker assessments	•	•			•	•	•	•			•			•
MGP, Osteocalcin, Activated Protein C, PIVKA-II protein, Fetuin A, osteoprotegerin, hs-CRP, and Time to Formation of Secondary Calciprotein		Х						Х			х			

	WEEK -1	WEEK 1 ON-TREATMENT			WEEK 2 ON-TREATMENT			WEEK 3 POST-TREATMENT			WEEK 4 POST-TREATMENT			EOS/ EARLY
VISIT SCHEDULE	Screening	1 BL	2	3	4	5	6	7 EOT	8	9	10	11	12	TERMINA TION
Study Day	-7 to -1	1	3	5	8	10	12	15	17	19	22	24	26	29
Day of the week		Mon	Wed	Fri	Mon	Wed	Fri	Mon	Wed	Fri	Mon	Wed	Fri	Mon
Particles (T-50 Test), including CPP size [16]														

Abbreviations: AE=adverse event; AESI=adverse event of special interest; ALT=alanine amino transferase; AST=aspartate amino transferase; BL=Baseline (visit); BUN=blood urea nitrogen; CMP=Complete Metabolic Panel; CPP=calciprotein particles; DNA=deoxyribonucleic acid; ECG=electrocardiogram; EOS=End-of-Study (visit); EOT=End-of-Treatment (visit); β-hCG=beta-human chorionic gonadotropin (pregnancy test); HDL=high-density lipoprotein; hs-CRP=high sensitivity C-reactive protein; INR=international normalized ratio; K=dialyzer clearance; LC/MS/MS=liquid chromatography tandem mass spectrometry; LDL=low-density lipoprotein; MGP=Matrix Gla protein; PK=pharmacokinetic(s); PTT=partial thromboplastin time; RBC=red blood cell (count); RNA= ribonucleic acid; SAE=serious adverse event; t=time; T-50 Test=Time to Formation of Secondary Calciprotein Particles; V=volume of urea distribution; WBC=white blood cell (count)

Note: Visit 1 will be the Baseline visit. End-of-Treatment (EOT) assessments will be completed after the last dose of study drug on study Day 15/Visit 7 (or earlier in case of an early discontinuation of the study treatment).

- [1] Demographic data include age, sex, and self-reported race/ethnicity.
- [2] General medical history includes clinically significant diseases (except those listed under "Disease history"), surgeries, reproductive status, and any conditions/symptoms present prior to the first dose of study drug.
- [3] Disease history includes details on the underlying condition, including renal (ESRD) and dialysis history.
- [4] A complete physical examination will be performed at screening and at the EOS visit on Day 29. A symptom-driven (abbreviated) physical examination may be performed at the EOT visit (Day 15), if the investigator deems it clinically indicated.
- [5] Subjects will undergo body weight and height measurement at screening/baseline, and body weight measurements (as part of their standard care on dialysis days) within 60 minutes pre-dialysis and within 60 minutes post-dialysis on each dialysis day during the 2-week treatment period (Visits 1 through 6), at the EOT visit (Day 15), and EOS visit (Day 29).
- [6] Standard 12-lead ECG recordings will be obtained within 60 minutes pre-dialysis at screening/baseline, at EOT (Day 15), and at EOS (Day 29). ECG recordings should be performed after the subject has been resting in a supine position for at least 5 minutes, and prior to other procedures scheduled at that same time (e.g., blood draws).

[7] Vital signs (including blood pressure, heart rate, respiratory rate, and oral body temperature) will be measured at screening, and (as part of their standard care on dialysis days) within 30 minutes pre-dialysis and within 30 minutes post-dialysis at each treatment visit (Visits 1 through 6), at EOT (Day 15), and EOS (Day 29).

- [8] All blood sampling will occur pre-dialysis (at the time of needle placement). Hematology panel includes: RBC count, hemoglobin, hematocrit, and WBC count with differential (neutrophils, eosinophils, lymphocytes, monocytes, basophils, and other cells), if clinically indicated. CMP includes: glucose, albumin, total protein, electrolytes (sodium, potassium, bicarbonate, chloride, calcium, magnesium, phosphate), renal function tests (BUN, creatinine), liver function tests (ALT, AST, bilirubin), and lipid profile (total cholesterol, LDL cholesterol, HDL cholesterol, and triglycerides). Coagulation panel includes: PTT, INR, and platelet count.
- [9] Serology for: HIV, HBV (hepatitis B "e" antigen [HBeAg] and PCR for the active virus [HBV DNA]); and HCV (HCV antibody and PCR for active virus [HCV RNA])
- [10] Women of child bearing potential must undergo a serum β-hCG pregnancy test within 7 days prior to the first dose of study drug, and the result must be negative for enrollment.
- [11] All medications (including over-the-counter medications) or therapy administered to the subject during the 30 days prior to the first dose of study drug will be recorded at screening/baseline. Any changes to concomitant medications will be documented regularly throughout the study.
- [12] All AEs with an onset between the time the informed consent is signed and 14 days after the last dose of study drug (EOS/Early Termination visit) are to be recorded on the appropriate Adverse Event CRF pages and in source documents. SAEs, AESIs, and pregnancies occurring during or within 30 days after the last dose of EPN-701 will also be reported in an expedited fashion. SAEs and AESI considered to be related to the study drug by the investigator, will be reported to the Sponsor even if they occurred after the protocol-specified reporting period (i.e., more than 30 days after the last dose of EPN-701). Any occurrence of dialyzer clotting (assessed at each dialysis session) is to be recorded as an AE.
- [13] EPN-701 10 mg per day (1 capsule of 10 mg). The study drug will be taken at approximately the same time each morning. On hemodialysis days (Days 1, 3, 5, 8, 10, and 12), subjects will take their study drug dose pre-dialysis (immediately after needle placement and biomarker sampling, as applicable); on the remaining days during Weeks 1 and 2, subjects will take their study drug dose at home.
- [14] Blood for PK assessments will be sampled as follows:
  - On Day 1 (baseline) and Day 8 (Week 2, on-treatment): pre-dialysis (at the time of needle placement, denoted as 0 hours), immediately followed by study drug administration, and then at 1 hour (+/- 5 minutes), 2 hours (+/- 5 minutes), 3 hours (+/- 5 minutes), 4 hours (+/- 30

minutes)/before needle removal, 6 hours (+/- 30 minutes), 8 hours (+/- 30 minutes), and 24 hours (+/- 60 minutes) after study drug administration;

- On Days 3, 5, 10, 12, and 15: pre-dialysis (at the time of needle placement, at 0 hours), immediately followed by study drug administration, and then at 4 hours (+/- 30 minutes)/before needle removal; and
- On Day 17 (Week 3, off-treatment): pre-dialysis only (at the time of needle placement).

Plasma levels of EPN-701 will be determined using a validated high-performance LC/MS/MS method.

[15] Kt/V (a standard measure of dialysis adequacy) will be calculated at baseline (as the average of the last three pre-study Kt/V values obtained as part of the subject's standard of care), and at EOT (Day 15). In case the Kt/V value obtained at EOT is reduced compared to baseline (pre-study measurements), the Investigator will determine (in consultation with the Medical Monitor, as needed) if the event qualifies for reporting as an AE.

[16] Blood sampling will always occur pre-dialysis (at the time of needle placement): on Day 1 (Baseline), Day 15 (EOT), and Day 22 (1 week after the last study drug dose), for a total of 3 samples collected. Plasma levels of the following biomarkers will be assessed: uncarboxylated MGP; uncarboxylated osteocalcin, Activated Protein C, PIVKA-II protein, Fetuin A, osteoprotegerin, *hs*-CRP, and Time to Formation of Secondary Calciprotein Particles (T-50 Test), including CPP size. Instructions for specimen collection and handling will be included in the laboratory manual provided by the Central Laboratory.

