# 9.3.5 Study Drug Dosage, Administration, and Compliance

EPN-701, the test product in this study, will be provided by the study sponsor at the following capsule dosage strength:

10 mg soft-gel capsule for oral administration.

Each subject will take one 10 mg capsule of EPN-701 per day orally over 14 days.

The study drug is to be taken at the same time each morning. On hemodialysis days (Days 1, 3, 5, 8, 10, and 12), subjects will take their study drug dose pre-dialysis (immediately after needle placement and biomarker sampling, as applicable); on the remaining days during Weeks 1 and 2, subjects will take their study drug dose at home.

Dose modifications of EPN-701 are not permitted during the study.

Any incorrect administration or overdose of the study drug should be noted on the eCRF. Adverse events associated with an incorrect administration or overdose of the study drug should be recorded on the Adverse Event eCRF.

Subject compliance with the study drug schedule must be assessed at the container/packaging level for unused investigational product that is contained within the original packaging, or at the individual count level for opened bottles. The pharmacist/designee will record details on the Study Drug Accountability Form.

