#### 9.6.8.3 Pharmacokinetic Assessments

Blood for PK assessments will be sampled as follows:

- On Visit 1/Day 1 (baseline) and Visit 4/Day 8 (Week 2, on-treatment): pre-dialysis (at the time of needle placement; denoted as 0 hours), followed by study drug administration, and then at 1 hour (+/- 5 minutes), 2 hours (+/- 5 minutes), 3 hours (+/- 5 minutes), 4 hours (+/- 30 minutes)/before needle removal, 6 hours (+/- 30 minutes), 8 hours (+/- 30 minutes), and 24 hours (+/- 60 minutes) after study drug administration;
- On Visit 2/Day 3, Visit 3/Day 5, Visit 5/Day 10, Visit 6/Day 12, and Visit 7/Day 15: pre-dialysis
  (at the time of needle placement, at 0 hours), immediately followed by study drug
  administration, and then at 4 hours (+/- 30 minutes)/ before needle removal; and
- On Visit 8/Day 17 (Week 3, off-treatment): pre-dialysis only (at the time of needle placement).

The timing and sequence of PK blood sample collections relative to the study drug administrations and dialysis will be as follows:

- PK samples taken pre-dialysis (pre-dose; at 0 hour): Samples will be collected after needle
  placement and will be immediately followed by the study drug administration. Immediately
  following drug administration, dialysis is to be started.
- PK samples taken during dialysis (post-dose): Samples will be collected at 1 hour (+/- 5 minutes), 2 hours (+/- 5 minutes) and 3 hours (+/- 5 minutes) after the 0-hour PK time-point.

[figure not shown]
\* Pre-dialysis=at the time of needle placement

- PK samples taken post-dialysis (post-dose): Samples will be collected when the dialysis is completed (before needle removal) or at 4 hours (+/- 30 minutes) after the 0-hour PK timepoint, whichever occurs first.
- Note: The duration of dialysis sessions is expected to be approximately 4 hours; however, the
  actual duration should not have an impact on the PK sample collection time-points.

The calendar date and actual clock time will be recorded for each PK blood sample collection and the actual elapsed time from dosing will be used for the PK calculations.

Refer to Figure 5 for further details.

Figure 5 - Sequence of PK Sampling, Visits 1 - 8

Plasma samples will be assayed for EPN-701 concentrations (ng/mL) according to standard procedures, using a validated high-performance liquid chromatography (HPLC) tandem mass spectrometric (LC/MS/MS) method.

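### The PK sampling instructions call for a Day 15 dose that the dosing instructions exclude, leaving the last dose day and the timing of two exploratory PK samples unsettled

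*Combined protocol and SAP*

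**What the plan says.** **Text that orders a Day 15 dose.** Table 1 note [14] reads: "On Days 3, 5, 10, 12, and 15: pre-dialysis (at the time of needle placement, at 0 hours), immediately followed by study drug administration", with a further sample at 4 hours or before needle removal. The synopsis has the same instruction. Section 9.6.8.3 repeats it by visit ("Visit 6/Day 12, and Visit 7/Day 15: pre-dialysis") and adds a general rule that pre-dialysis PK samples are taken after needle "placement and will be immediately followed by the study drug administration". That rule makes no exception for Day 15, or for Day 17, which is off treatment.

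**Text that excludes a Day 15 dose.**
- Section 9.3.5: "Each subject will take one 10 mg capsule of EPN-701 per day orally over 14 days".
- Table 1 note [13], and Section 9.3.5 in the same terms: "On hemodialysis days (Days 1, 3, 5, 8, 10, and 12), subjects will take their study drug dose pre-dialysis". Day 15 is a dialysis day and is not listed.
- Table 1: the drug row runs from Day 1 through Day 14, and Day 15 stands under the header "WEEK 3 POST-TREATMENT".
- Section 9.5.2, which covers Visits 1, 4, 7 and 10, restricts study drug to Visits 1 and 4. Visit 7 is Day 15.

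**Text that does not settle it.** The end-of-treatment wording in the synopsis, the Table 1 note, Section 8.1 and Section 9.5.2 can mean either that the assessments fall on Day 15 or that the last dose does. Section 9.6.8.2 places Day 22 one week after the last dose, and Section 8.1 places Day 29 two weeks after it. Both intervals count from Day 15.

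**The concern.** These are current operative instructions, and they give opposite answers to a simple question: does the subject take a capsule at Visit 7? A site that doses departs from Sections 9.3.5 and 9.5.2. A site that does not dose departs from Section 9.6.8.3. Section 10.3.2 makes incorrect administration a protocol deviation and Section 10.4.1 makes medication errors reportable within 24 hours, yet the protocol does not establish which action would be the error.

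The statistical stake is narrower. Section 11.7 summarizes concentrations by assessment time point. If sites or subjects differ in what they do on Day 15, the Day 15 end-of-dialysis row and the Day 17 row would each mix two different times since the last dose.

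**Working it through.** **Inputs.** Dosing days: Table 1 and Section 9.3.5. PK schedule: Table 1 note [14] and Section 9.6.8.3. Blood volume: Section 9.6.8.3. Number of subjects: 15 (Section 8.1). Half-life of MK-7: 72 h (Section 6.1.2) and 68 h (Section 6.2.3).

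**1. The plan's own figure.** PK samples per subject:
- Days 1 and 8: 2 × 8 = 16
- Days 3, 5, 10, 12 and 15: 5 × 2 = 10
- Day 17: 1

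The total is 16 + 10 + 1 = 27, and 27 × 4 mL = 108 mL, the stated volume. The second Day 15 sample is therefore planned on either reading, so the volume does not show which reading is meant.

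**2. Number of doses.**
- Dosing text: clinic Days 1, 3, 5, 8, 10, 12 (6) plus home Days 2, 4, 6, 7, 9, 11, 13, 14 (8) = 14 doses; 14 × 10 mg = 140 mg.
- PK text: 7 clinic + 8 home = 15 doses; 15 × 10 mg = 150 mg.

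The difference is 10 mg, or 10/140 = 7.1%. The daily dose stays 10 mg.

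**3. Time since last dose**, taking every dose at about the same clock time:

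| Assessment | Last dose Day 14 | Last dose Day 15 |
|---|---|---|
| Day 15 pre-dialysis | 24 h | 24 h after the Day 14 dose (sample precedes the new dose) |
| Day 15 end of dialysis | 24 + 4 = 28 h | 4 h |
| Day 17 pre-dialysis | 3 × 24 = 72 h | 2 × 24 = 48 h |
| Day 22 | 8 days | 7 days |
| Day 29 | 15 days | 14 days |

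**4. Share of PK samples affected.** Two per subject: 2 × 15 = 30 of 27 × 15 = 405, or 7.4%.

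**5. What 24 hours could mean for the concentrations (illustrative).** Section 6.2.3 describes a peak at about 4 h and then a steep decline, so the Day 15 end-of-dialysis sample is near the peak on one reading and beyond a 24 h trough on the other. For Day 17, assuming simple exponential decline, the 72 h level relative to the 48 h level is 2^(−24/68) = 0.78 to 2^(−24/72) = 0.79, so 21–22% lower. The half-lives are published MK-7 values, not data on EPN-701 in this population.

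**The case against.** The strongest reply is that the dosing sections agree with one another and the outlier is a blood-sampling sentence, repeated in three places, that groups Day 15 with four on-treatment days. Section 8.1.1 sends sites to Section 9.5 for what to do at each visit, and Section 9.5.2 excludes Visit 7. Supply is for two weeks. Section 9.3.6 has doses documented, including date, time and amount for those taken at home. Section 9.6.8.3 records the clock time of each sample and states that the "actual elapsed time from dosing will be used for the PK calculations". Each subject's true post-dose time is thus recoverable, and all data are listed by subject.

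Much of this stands. Fourteen doses is probably the intention, PK calculations are protected, and the two samples are not equally affected: Day 15 end of dialysis changes far more than Day 17. Counting only the former gives 15 of 405, or 3.7%. Section 8.1's description of that sample as post-dose is also tolerable, since a 28 h sample still follows a dose.

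It does not remove the conflict. Recorded times show afterwards what was done; they do not tell a site what to do. The supply is no barrier either: no capsule count is given, and Section 9.5.2 hands it over at the end of Visit 1, after the Day 1 clinic dose, so two weeks' supply could cover Days 2 to 15. The Day 22 and Day 29 intervals fit a Day 15 last dose exactly. Section 9.6.8.3 says "Refer to Figure 5 for further details", and that figure is not visible in the text available here. It might show the intended sequence, but it cannot reconcile sentences that contradict each other.

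**Conclusion.** The concern holds. It is an internal inconsistency about whether a dose is given on Day 15, and it should be fixed. Its size is one 10 mg capsule per subject and two exploratory PK samples per subject (30 of 405, 7.4%), each uncertain by 24 hours. The two descriptive rows would be mixed only if practice differs between sites or subjects. The hour figures assume that the Day 14 home dose is taken at about the clinic dosing time.

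Not affected: the primary endpoint of treatment-emergent adverse events, adverse event recording through Day 29, the Day 15 biomarkers, the Day 15 pre-dialysis PK sample, the Day 1 and Day 8 profiles, and PK calculations based on actual elapsed time. No safety harm is shown.

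**What to change.** State once, plainly, that the last dose is on Day 14. Then:
- In the synopsis, Table 1 note [14] and Section 9.6.8.3, take Day 15 out of the bullet that includes dosing. List it separately as a day without a dose, with samples about 24 h and 28 h after the Day 14 dose, and describe Day 17 as about 72 h after it.
- Limit the general sequence rule in Section 9.6.8.3 to Days 1, 3, 5, 8, 10 and 12.
- Reword the end-of-treatment sentences in the synopsis, the Table 1 note, Section 8.1 and Section 9.5.2 so that the assessments fall on Day 15, the day after the last dose.
- Give Days 22 and 29 as 8 and 15 days after the last dose, and check that Figure 5 agrees.
- Optionally, drop the post-dose label for Day 15 in Section 8.1.

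If 15 doses are intended, change the dosing sections, the Table 1 drug row and the supply statement to say so instead.

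The cost is protocol wording. No samples, visits or subjects are added, and the 108 mL of PK blood is unchanged. Once the last dose day is fixed, the tabulation in Section 11.7 can stay as it is.
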